## 2.5 Risk/Benefit Assessment

### 2.5.1 Known Potential Risks

Most adverse drug reactions seen with the immune checkpoint inhibitor class of agents are thought to be due to the effects of inflammatory cells on specific tissues. These risks are generally events with a potential inflammatory or immune mediated mechanism,

and which may require more frequent monitoring and/or unique interventions such as immunosuppressants and/or endocrine therapy. These immune mediated effects can occur in nearly any organ system, and are most commonly seen as gastrointestinal AEs such as colitis and diarrhea, pneumonitis/interstitial lung disease (ILD), hepatic AEs such as hepatitis and liver enzyme elevations, skin events such as rash and dermatitis, and endocrinopathies including hypo- and hyper-thyroidism.

Risks with durvalumab include, but are not limited to, diarrhea/colitis, pneumonitis/interstitial lung disease (ILD), endocrinopathies (ie, events of hypophysitis/hypopituitarism, adrenal insufficiency, hyper- and hypothyroidism, type I diabetes mellitus (which may present with diabetic ketoacidosis), and diabetes insipidus), hepatitis/increases in transaminases, nephritis/increases in creatinine, rash/dermatitis (including pemphigoid), myocarditis, myositis/polymyositis, immune thrombocytopenia, infusion related reactions, hypersensitivity reactions, pancreatitis, encephalitis, serious infections, subcutaneous injection site reaction, and other rare or less frequent inflammatory events including neuromuscular toxicities (eg, Guillain-Barré syndrome, myasthenia gravis)

For information on all identified and potential risks with durvalumab please always refer to the current version of the durvalumab IB.

The potential adverse effects (AEs) of the systemic therapy regimen of cisplatin or carboplatin plus etoposide together with durvalumab were reported in the results of the CASPIAN study (see Appendix A). Specifically, AEs of any cause and grade occurred in 98% of subjects treated with durvalumab plus platinum-etoposide, while 62% of those in this study arm developed any grade 3 or 4 AE, the most common of which were neutropenia and anemia. Only 9% of subjects developed an AE that lead to discontinuation of therapy, however. Deaths due to AE of any cause occurred in 5% of subjects, similar to that in the standard platinum-etoposide group. Immune-mediated AEs (ImAEs) occurred in 20% of subjects treated with durvalumab plus platinum-etoposide, with only 5% being grade 3 or 4. The most common ImAEs were hypo- and hyperthyroidism. Death due to ImAE occurred in <1% of subjects (1 subject – due to hepatotoxicity).

A primary objective of this study is to evaluate the risks of adding non-ablative radiation to the above treatment regimen. Potential risks which the study will focus on will be an increase in ImAEs (other than thyroid dysfunction, which is generally easily managed), and an increase in radiation-related AEs, specifically pneumonitis, pericarditis, esophagitis, rib fracture, and hemoptysis. The reported rates of pneumonitis after SBRT requiring intervention range from 0-29%, with an uncommon occurrence of severe ( $\geq$  grade 3) pneumonitis. Reported cardiac events associated with SBRT occur in 0-7.9% of treated patients. Chest wall related toxicities after SBRT include skin toxicity (1.2-14%), rib fracture (5%) and chronic chest wall pain (5-25%) and are usually associated with peripherally located lung tumors. Esophageal injury ranging from mild esophagitis to stricture, perforation, and/or fistula formation has been reported to occur in 12% of patients treated with SBRT. Finally, with standard fractionation schemes fatal hemoptysis secondary to aortic damage, rupture, aneurysm, or aortic dissection may occur in up to 5.7% of patients, particular for those that receive a maximum composite dose to 1cm^3 of the aorta  $\geq$  120Gy (25% rate of grade 5 toxicity) versus < 120Gy (0% rate of grade 5 toxicity). Similar cases have been reported with

SBRT. Currently, 50Gy delivered over five fractions has been a widely adopted SBRT regimen for treatment of centrally located tumors and tumors close to the chest wall. Less intensive SBRT fractionation schemes or risk-adapted approaches further limits toxicities and provides for a safer approach. For this study, we have chosen a conservative regimen of 25-30Gy delivered over five fractions (less than the commonly used 50Gy delivered over five fractions regimen). While this radiation will be delivered via SBRT whenever feasible, radiation via 3D-CRT and IMRT will also be permitted..

### **2.5.2 Known Potential Benefits**

The potential benefit of the systemic therapy regimen of cisplatin or carboplatin plus etoposide together with durvalumab were reported in the results of the CASPIAN study and are outlined in the background section of this protocol. We hypothesize that the addition of radiation to one or more sites of disease will enhance the efficacy of systemic chemotherapy plus immunotherapy, improving 12-month progression free survival and possibly also response rates and median progression-free and overall survival. This hypothesis is based on data outlined in the background section which have shown that radiation in dosages similar to those used in this protocol can augment checkpoint-inhibitor-induced, immune-mediated killing of non-small cell lung cancer. This includes unpublished preliminary data from our clinical trial of neoadjuvant durvalumab with or without non-ablative SBRT for the pre-operative treatment of stage I, II, and IIIA NSCLC (<https://clinicaltrials.gov/ct2/show/NCT02904954>) and our clinical trial of ipilimumab plus nivolumab with non-ablative SBRT for stage IV NSCLC (<https://clinicaltrials.gov/ct2/show/NCT03168464>).

### **2.5.3 Assessment of Potential Risks and Benefits**

Given known safety profiles of systemic therapy with platinum-etoposide plus durvalumab systemic therapy, as well as those of non-ablative radiation, we believe that the combination of these two approaches will be safe and feasible in this study population of patients with treatment-naïve ES-SCLC. As safety will be a primary objective of this study, the subjects will be monitored closely for adverse events, which will be a primary endpoint of the trial. The study includes a safety run-in period involving the first 10 subjects enrolled wherein if there is a 30% or greater incidence of grade 3 or higher toxicities with the radiation regimen of 6 Gy per day for 5 fractions - specifically from radiation therapy or ImAEs (other than thyroid dysfunction) - then the radiation regimen will subsequently be switched to 5 Gy radiation per day for 5 fractions. If there is still a 30% or greater incidence of grade 3 or higher toxicities from radiation therapy or ImAEs adverse events among the subsequent 10 subjects, then the study will be terminated.

We therefore believe that the potential value of the information gained from this trial and the potential for improvement in outcomes will likely outweigh the possible increased risk to participants.

## **2.6 Correlative Studies Background**

### **2.6.1 Tumor-Immune Microenvironment and Circulating Immune Cells/Inflammatory Proteins**

An anti-tumor immune response is dependent on the appropriate balance of activities

from effector cells and suppressor cells in the tumor-immune microenvironment. ICB therapies can alter the compositions of circulating and tumor-infiltrating immune cells and these compositions can correlate with treatment response. Additionally, radiation therapy to tumors causes accumulation of DNA in the cytoplasm of irradiated cells which in turn leads to the activation of the cyclic GMP-AMP synthase (cGAS)/stimulator of interferon genes (STING) pathway, with the resultant production of type 1 interferon (IFN) and other pro-inflammatory cytokines. These cytokines also play a role in tumor-immune response. Other cytokines and soluble factors that can be increased by radiation therapy may be associated with immune suppression (e.g., soluble MICA/B, soluble CD73).

We therefore will plan to examine the tumor-immune microenvironment and the circulating immune cell and inflammatory protein composition in the study subjects, as correlative studies. Specifically, we will isolate peripheral blood mononuclear cells (PBMCs) and examine them for frequencies of CD4+ T cells, CD8+ T cells, natural killer (NK) cells, myeloid-derived suppressor cells (MDSCs), T regulatory cells (Tregs), macrophages, and dendritic cells (DCs). We will specifically examine Ki67+PD-1+ CD8 T cells with an effector-like phenotype (HLA-DR+CD38+Bcl-1low) since they have been shown to be predictive of response in lung cancer patients treated with anti-PD-1 when increased within 4 weeks of treatment start from baseline by two to seven-fold. We will also quantify cytokine levels in the peripheral blood of subjects, particularly type-1 IFN. Additionally, if we are able to obtain sufficient tissue from biopsy samples, we will examine the frequencies of tumor-infiltrating lymphocytes (TILs) in these samples, as well as the T cell receptor (TCR) repertoire of the CD8+ T cells from the TILs and the PBMCs. These studies may provide insight into the mechanisms of immune response and resistance to the treatment modalities used in this study.

### 2.6.2 Tumor Organoids

As part of the Englehardt Institute for Precision (EIPM) at Weill Cornell Medicine, the Tumor Organoid Platform is an active program focused on development of 3D patient derived tumor organoids (PDTO) from metastatic and primary anatomic sites, obtained through biopsies, surgical resections and rapid autopsy procedures. The fresh tissue is obtained through our IRB-approved precision medicine clinical trial where full patient consent is obtained for both organoid and xenograft development. Standard operation procedures are in place for all aspects of tissue processing and culture maintenance. In this setting, we are able to extend our personalized medicine program to include high throughput and/or targeted drug screening which can be validated through histologic examination and genomic sequencing, and both *in vivo* and *in vitro* models. To date, we have established in our biobank, more than a 100 3D PDTOs, spanning a range of 13 primary tumor types that can be used for a variety of experiments and co-clinical trials (Figure 1).

In our recent publications, PDTO samples have demonstrated high purity as well as ploidy and genomic burden profiles that matched patient tumor data. Allele-specific copy-number analysis of 1,062 putative cancer genes showed a median of 86% concordance when comparing PDTOs to the native tumor tissues. Minor differences observed are either due to subclonality in the native tumor (subclones not represented in the PDTO) or due to the progression of the PDTO/PDX. Similarly, SNV analysis showed excellent concordance between native tumors and matching PDTOs. We have demonstrated that

these specimens can be successfully thawed and reestablished in culture for use in scientific research. Organoid technologies are developed in a dedicated space which is comprised of 3 four-foot biosafety cabinets, 6 Panasonic incubators, a Beckman Coulter centrifuge, an Olympus inverted microscope (CKX53), Olympus DP73 camera and Cell Sense Imaging Software, VWR water bath and a Thermo Scientific, MaxQ 4450 incubated shaker.

The EIPM's new high throughput drug screening platform is an integrative robotics system that connects some of the most coveted laboratory equipment on the market into a fully modular, HEPA filtered unit. With capabilities such as high content imaging, endpoint reads using a variety of PMT channels, in house static and dynamic incubator systems, a centrifuge and a state of the art liquid handler connected by two robotic arms and a powerful scheduling software, fully customized experiments can be run in their entirety in a sterile environment. Instrument software is scheduled to be 21CFR.11 compliant by the end of 2021 and it is our goal to develop our platform into a CLIA certified testing facility.

The Operetta CLS high content imaging system enables live cell experiments, 3D imaging, and high resolution and fast read times. Associated with Harmony software which is specifically designed for 3D cell models, the Operetta is capable of sensitive and quantitative measurements that can be used as a stand-alone reader or incorporated into our high throughput automation system. Spinning disk confocal optics and synchronized LED illumination provide stable excitation and minimize phototoxicity and bleaching for meaningful live-cell assays. A large format sCMOS camera with water-immersion objectives provides high resolution, while the software addresses the imaging and analysis challenges presented by complex cellular models.

Over the last few months we have been optimizing and validating image-based cell viability measurements using our previously biobanked organoids. The validation was done against an endpoint metabolic measure of ATP production. For this, one of our established colorectal lines, PM1230, which was shown to have a mutation in KRAS was treated with the MEK inhibitor Trametinib. A dose response curve starting at 3 $\mu$ M with an 8-point dilution of 1:3 was compared to an untreated control (DMSO). Duplicate experiments were run in parallel; one for the purpose of imaging and the other for cell titer glo measurement of cell metabolism. After 4 days of treatment, NucBlue and Cell Mask were added to the plates slotted for image analysis, after which they were incubated for 1 hour at 37°C. A pre-scan analysis was performed at a magnification of 5X (air) to pre-select an unbiased population of organoids utilizing instrument based software features. Selected organoids were then re-scanned at 63X (water-immersion), using z-stack analysis tools in order to perform 3D image analysis. As shown in Figure 2, both methods exhibit the same drug response. Although further optimization is required to reach the full potential of this platform, these results are a promising use of high content imaging as a complement to the indirect measure of viability using Cell Titer Glo.

As proof-of-concept, we have already generated and banked 15 lung PDTOs from treatment naïve Non-Small Cell Lung Cancer patients. Targeted sequencing of the initial lung PDTOs lines showed they contain cancer driver mutations (KRAS, EGFR and P53), confirming that our growth conditions are optimized for lung cancer organoids (Figure 3). In this study we will focus on growing organoids from Small Cell Lung Cancer patients.

3.

[figure not shown]
[figure not shown]
[figure not shown]

Figure 1. Patient-derived tumor organoid biobank at Engleander Institute for Precision Medicine

**Figure 2.** Optimization of the high throughput imaging platform. (A) Representative brightfield (upper panel) and NucBlue (lower panel) pictures of a colorectal organoid line (PM1230) treated with a dose response of Trametinib, a K-Ras inhibitor (starting at 3  $\mu\text{M}$  with a 3-dilution factor). The pictures were taken with a 5X air objective (B) Quantification of organoid volume ( $\mu\text{m}^3$ ) using our high content system Operetta in combination with Harmony Software based on 3D imaging of NucBlue. (C) Viability measurement of organoid line PM1230 in a parallel experiment to (A) using Cell Titer Glo 3D, which measures ATP production. Data was normalized to control (untreated) and represents meanSEM. (D) Representative pictures of PM1230 colorectal organoids at 63X magnification stained with NucBlue (Blue) and CellMask (Red).

**Figure 3** Representative brightfield picture of Non-Small Cell Lung tumor organoids cultured in matrigel.

### 2.6.3 Circulating Tumor Cells

A technical limitation of studies aimed to understand molecular determinants of therapeutic response in cancer cells is the availability of tumor tissue. First, the invasive nature of biopsies often prevents longitudinal analysis of the dynamic response of cancer and immune cells to the treatment. Second, tissue derived from the biopsy of a single tumor site may not recapitulate the entire tumor biology. This lack of tumor material, together with the inability to perform serial tumor biopsies, limits extensive and longitudinal investigation of the molecular determinants of tumor response to treatment and disease progression.

To overcome these limitations, we will utilize circulating tumor cells (CTCs) as a source of tumor material to investigate the molecular response of tumor cells to the proposed treatment. To date, most CTC enrichment methodologies (including the only FDA-cleared method, CellSearch), utilize the Epithelial Cell Adhesion Molecule (EpCAM) as a positive selection CTC marker. Several studies reported that CellSearch successfully identifies CTCs in SCLC patients and that EpCAM-based CTC enumeration yields prognostic significance. EpCAM+-CTCs have been previously utilized to interrogate the molecular characteristics of SCLC as they can recapitulate clinical response to chemotherapy in patients. However, EpCAM expression is significantly reduced or even lost during the epithelial-mesenchymal transition (EMT), a key process in cancer progression during which metastatic capability is acquired. Therefore, the population of EpCAM+-CTCs represents only a subpopulation of CTCs, limiting their biological relevance and clinical use. To help overcome this limitation in NSCLC patients, [name] lab identified Transferrin Receptor (TfR) as an alternative cell-surface antigen that can be used to capture CTCs across the EMT gradient. TfR is a cell surface protein that mediates intracellular iron uptake by binding to the iron carrier transferrin. This protein is expressed at low levels in many normal tissues but it is significantly over-expressed in cancer cells, including NSCLC cells. However, it is unclear if this protein is overexpressed in SCLC tumors and CTCs, though we are currently assessing this in the lab.

As a correlative study of this trial, we will prospectively and longitudinally isolate and molecularly analyze CTCs and matching peripheral blood mononuclear cells (PBMCs) from subjects receiving the combination of chemo-immunotherapy and non-ablative radiation. The goal of our analysis is to identify genes/pathways associated with clinical response/resistance to this treatment by performing untargeted RNA sequencing of patient-derived-CTCs (tumor compartment) with matching PBMCs (immune compartment).

To overcome the limitations intrinsic to an EpCAM-based positive selection, we will enrich CTCs by using the antigen-agnostic RosetteSep™ Circulating Epithelial Tumor Cells

enrichment assay (STEMCELL™ Technologies); this approach utilizes anti-CD45/antiglycophorin A antibody complexes that crosslinks red blood cells (glycophorin A+) and white blood cells (CD45+), which are subsequently eliminated by gradient-based separation. Such antigen agnostic approach allows the enrichment of a pool of heterogeneous subpopulation of CTCs compared to traditional approaches that rely on positive selection of epithelial markers (i.e. EpCAM). Additionally, if work in the lab shows that SCLC CTCs express TfR (as NSCLC CTCs do), then we will also attempt to use this marker to help isolate CTCs from the subjects in this study.

Gene set enrichment analysis of differentially expressed genes between baseline, on-treatment, and relapse CTCs will be performed to identify pathways associated with onset of resistance to the treatment. To assess immune cell activation induced by treatment, matched PBMCs will be isolated from the above and gene expression analysis will be performed. Gene set enrichment analysis of differentially expressed genes between baseline and on treatment will reveal immune signatures characterizing host immune activation as a consequence of the treatment and will identify immune components that discriminate responders from non-responder patients.

### **3. Study Design**

#### **3.1 Overall Design**

This is a prospective, non-randomized, open-label, single-arm pilot phase II study of non-ablative radiation in combination with standard-of-care chemo-immunotherapy in patients with untreated, extensive-stage small cell lung cancer. The hypothesis of this study is that the addition of sub-ablative doses of radiation to combination chemotherapy and immunotherapy will be safe and feasible and result in improved outcomes for patients with treatment-naive, extensive-stage small cell lung cancer.

The study will plan to enroll 42 subjects across 3 sites to allow for 34 subjects to be evaluable for the primary endpoints. All subjects will be treated with etoposide plus platinum (carboplatin or cisplatin) chemotherapy together with the PD-1 checkpoint inhibitor durvalumab, which is a standard of care in this disease setting. All subjects will also receive a total of 6 Gy of radiotherapy per day for 5 fractions. Radiation will start prior to the completion of the second cycle of chemo-immunotherapy but will ideally begin on the first day of the first cycle; no further radiation will be planned after this.

There will be a safety run-in period involving the first 10 subjects enrolled wherein if there is a 30% or greater incidence of grade 3 or higher toxicities with the proposed treatment regimen - specifically from radiation therapy (with focus on pneumonitis, pericarditis, esophagitis, rib fracture, or hemoptysis) or immune-mediated adverse events (other than thyroid dysfunction) - then the radiation regimen will subsequently be switched to 5 Gy radiation per day for 5 fractions. If there is still a 30% or greater incidence of grade 3 or higher toxicities from radiation therapy or immune-mediated adverse events among the subsequent 10 subjects, then the study will be terminated. If this does not occur, then accrual will continue until 34 total subjects are evaluable.

Systemic therapy will be given as follows:

- Carboplatin at AUC = 5-6 mg/mL per min or Cisplatin at 75-80mg/m^2 on Day 1 of each 21-day cycle, for 4 cycles

- Etoposide at 80-100mg/m^2 on Day 1, Day 2, and Day 3 of each 21-day cycle, for 4 cycles
- Durvalumab at 1500mg on Day 1 of each 21-day cycle, for 4 cycles; following this, subjects will receive 1500mg Durvalumab once every 4 weeks until disease progression.

Treatment will continue until disease progression, intolerance due to toxicity, or withdrawal of consent. Prophylactic Cranial Irradiation (PCI) and consolidative Thoracic Radiotherapy (TRT) will not be given.

This study will enroll subjects at NewYork Presbyterian Hospital-Weill Cornell Medicine.

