endpoints. All subjects will be treated with etoposide plus platinum (carboplatin or cisplatin) chemotherapy together with the PD-L1 checkpoint inhibitor durvalumab, which is a standard of care in this disease setting. All subjects will also receive a total of 6 Gy of radiotherapy X 5 fractions via 3D-CRT, IMRT, or SBRT and targeting multiple sites of intrathoracic disease when feasible and/or any site required for palliation of symptoms. Radiation will start prior to the completion of the second cycle of chemo-immunotherapy but will ideally begin on the first day of the first cycle; no further radiation will be planned after this. There will be a safety run-in period involving the first 10 subjects enrolled wherein if there is a 30% or greater incidence of grade 3 or higher toxicities with the proposed treatment regimen - specifically from radiation therapy (with focus on pneumonitis, pericarditis, esophagitis, rib fracture, or hemoptysis) or immune-mediated adverse events (other than thyroid dysfunction) - then the radiation regimen will subsequently be switched to 5 Gy radiation per day for 5 fractions.

Systemic therapy will be given as follows:

- Carboplatin at AUC = 5-6 mg/mL per min or Cisplatin at 75-80mg/m^2 on Day 1 of each 21-day cycle, for 4 cycles
- Etoposide at 80-100mg/m^2 on Day 1, Day 2, and Day 3 of each 21-day cycle, for 4 cycles
- Durvalumab at 1500mg on Day 1 of each 21-day cycle, for 4 cycles; following this, subjects will receive 1500mg Durvalumab once every 4 weeks until disease progression.

Prophylactic Cranial Irradiation (PCI) and consolidative Thoracic Radiotherapy (TRT) will not be given.

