### **6.1.2 Treatment Phase**

#### **6.1.2.1 Cycle 1 Day 1 (Day 1)**

- Interval Medical History
- Concurrent Medications
- Vital signs including Height and Weight
- Physical Exam
- Labwork: CBC with differential; Serum Chemistry with Liver Function Tests; Amylase and/or Lipase; Thyroid Function Panel; beta-hCG (for pre-menopausal females)
- Blood for Correlative Studies
- Fraction 1 (6 Gy) of radiation (when feasible) – repeat 6 Gy for total of 5 fractions; fractions do not need to be given on consecutive days but all

attempts should be made to do so. When feasible, radiation should be given before chemo-immunotherapy on any given day. Radiation may start after Cycle 1 Day 1 but not after Cycle 2 Day 3

- Carboplatin AUC = 5-6 mg/mL per min IV or Cisplatin 75-80mg/m^2 IV on D1
- Etoposide 80-100mg/m^2 IV on D1, D2, and D3
- Durvalumab 1500mg IV on D1

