### **12. Statistical Considerations**

#### **12.1 Study Design/Endpoints**

One primary aim of this study is to demonstrate that the addition of radiation to chemotherapy and immunotherapy is associated with an improvement in 12-month PFS from 18% historical control to approximately 38% with the addition of radiation. With a sample size of 34 patients receiving chemotherapy/immunotherapy plus radiation, a one-group chi-square test will have 80% power to detect the difference between a null hypothesis 12-month PFS proportion of 18% (i.e., historical control) and an alternative hypothesis 12-month PFS proportion of 38% (i.e., chemotherapy + immunotherapy + radiation), with a 0.05 two-sided significance level. As well, a sample size of 34 patients will allow a two-sided 95% confidence interval for the expected 12-month PFS proportion (38%) to be constructed to be within  $\pm 16.3\%$  of the observed 12-month PFS proportion.

The second primary aim of this study is to evaluate the safety of combining carboplatin + etoposide chemotherapy, durvalumab immunotherapy, and non-ablative radiation to one or more sites of disease. Due to this, we propose a safety run-in for the first 10 subjects. If there is a 30% or greater incidence of grade 3 or higher toxicities with the proposed treatment regimen, specifically from radiation therapy (with focus on pneumonitis, pericarditis, esophagitis, rib fracture, or hemoptysis) or immune-mediated adverse events (other than thyroid dysfunction), then the radiation regimen will be switched to 5 Gy radiation per day for 5 days. If there is still a 30% or greater incidence of grade 3 or higher toxicities from radiation therapy or immune-mediated adverse events among the subsequent 10 subjects, then the study will be terminated. If this does not occur, then accrual will continue until 34 total subjects are evaluable.

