### **12.6 Reporting and Exclusions**

#### **12.6.1 Evaluation of Toxicity**

All subjects will be evaluable for toxicity from the time of their first treatment with carboplatin or cisplatin with etoposide and durvalumab or their first radiation fraction.

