### **14.1 Stopping Rule**

If there is a 30% or greater incidence of grade 3 or higher toxicities with the proposed treatment regimen in the first 10 subjects, specifically from radiation therapy (with focus on pneumonitis, pericarditis, esophagitis, rib fracture, or hemoptysis) or immune-mediated adverse events (other than thyroid dysfunction), then the radiation regimen will be switched to 5 Gy radiation per day for 5 days. If there is still a 30% or greater incidence of grade 3 or higher toxicities from radiation therapy or immune-mediated

adverse events among the subsequent 10 subjects, then the study will be terminated. If this does not occur, then accrual will continue until 34 total subjects are evaluable.

If safety concerns arise, the DSMB will identify these concerns and recommend modification or termination of the clinical trial.

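### The run-in that sets the radiation dose counts the first 10 subjects enrolled, whether or not they were irradiated; any who never were make the 3-of-10 trigger less sensitive

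*Combined protocol and SAP*

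**What the plan says.** The run-in rule appears in five places. Section 3.1 says "There will be a safety run-in period involving the first 10 subjects enrolled", section 1 "There will be a safety run-in period involving the first 10 subjects enrolled wherein", and section 2.5.3 "The study includes a safety run-in period involving the first 10 subjects enrolled". Section 12.1 has "we propose a safety run-in for the first 10 subjects" and section 14.1 "with the proposed treatment regimen in the first 10 subjects". The events counted are grade 3 or higher radiation toxicities and immune-mediated events other than thyroid dysfunction. An incidence of 30% or more, which is 3 of 10, switches the regimen from 6 Gy x 5 to 5 Gy x 5. The same incidence in the following 10 subjects terminates the study.

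Four other provisions bear on who is counted:

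- Section 6.1.2.1: "Radiation may start after Cycle 1 Day 1 but not after Cycle 2 Day 3". A subject can therefore have a full cycle of chemotherapy and durvalumab before any fraction.
- Section 8.2: subjects who consent but never receive the study intervention may be replaced. Those who receive it and then leave are not.
- Section 12.6.1: toxicity is evaluable from first treatment with "carboplatin or cisplatin with etoposide and durvalumab or their first radiation fraction".
- Section 12.6.2: completed radiation is required, but only for response assessment.

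**The concern.** The first-stage decision concerns only the radiation dose, so its denominator should be people exposed to that dose. Followed literally, the rule also counts a subject who received chemo-immunotherapy and left before the first fraction. That subject cannot have radiation pneumonitis, esophagitis or any other radiation toxicity, and contributes only the background risk of a severe immune-mediated event. Section 7 lists chemotherapy and durvalumab under study intervention, so the most natural reading of section 8.2 is that this subject is not replaced.

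The error runs one way. Whenever radiation adds risk, unirradiated subjects make the dose look safer than it is. The cohort has only 10 people, this is the only numerical trigger for the safety co-primary aim, and the cohort that decides termination has the same gap.

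**Working it through.** **The plan's own figure.** The only design calculation stated is for efficacy: n = 34 gives 80% power for 18% versus 38%, two-sided 0.05. It reproduces: [(1.960 x sqrt(0.18 x 0.82) + 0.842 x sqrt(0.38 x 0.62)) / 0.20]^2 = 33.7, rounded up to 34. It does not bear on this point. The plan states no operating characteristics for the run-in, so they are computed here.

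**Inputs.**

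- Cohort of 10, trigger at 3 or more (3.1, 12.1, 14.1).
- p: true qualifying-event rate in irradiated subjects. This is an assumption, shown at 20%, 30% and 40%.
- q: rate of qualifying events in unirradiated subjects, taken as 0% to 5%. Section 2.5.1 gives 5% for grade 3-4 immune-mediated events in the historical control. Table S8 in Appendix A gives 12/265 = 4.5%, none of them thyroid; adding the one fatal case makes at most 13/265 = 4.9%.
- k: unirradiated subjects among the 10. This is an assumption, 0 to 2; the documents give no figure.

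**Formula.** P(X >= 3), where X = Bin(10 - k, p) + Bin(k, q).

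**Worked at p = 30%.**

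- k = 0: 1 - 0.0282 - 0.1211 - 0.2335 = 0.617.
- k = 1, q = 0: 1 - 0.0404 - 0.1556 - 0.2668 = 0.537. With q = 5%, add 0.05 x 0.2668 = 0.013, giving 0.551.
- k = 2, q = 0: 1 - 0.0576 - 0.1977 - 0.2965 = 0.448. With q = 5%, add 0.0975 x 0.2965 + 0.0025 x 0.1977 = 0.029, giving 0.478.

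**Chance of triggering (range is q = 0% to 5%).**

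| True rate p | 10 irradiated | 9 irradiated | 8 irradiated |
|---|---|---|---|
| 20% | 32.2% | 26.2-27.7% | 20.3-23.3% |
| 30% | 61.7% | 53.7-55.1% | 44.8-47.8% |
| 40% | 83.3% | 76.8-77.6% | 68.5-70.5% |

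At p = 30%, each unirradiated subject costs about 7 to 9 percentage points. If p equals q there is no loss: at 5% for both, the chance is 1.15% for every k.

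**Effect of correcting the denominator.** Suppose a fraction f of enrolled subjects is never irradiated and q = 5%. The literal rule has rate r = (1 - f)p + 0.05f per counted subject and triggers with probability P(Bin(10, r) >= 3). The corrected rule uses Bin(10, p).

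| True rate p | Literal, f = 10% | Literal, f = 20% | Corrected |
|---|---|---|---|
| 10% | 6.2% (r = 0.095) | 5.4% (r = 0.09) | 7.0% |
| 20% | 27.7% (r = 0.185) | 23.4% (r = 0.17) | 32.2% |
| 30% | 54.8% (r = 0.275) | 47.4% (r = 0.25) | 61.7% |

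Expected enrolment to fill 10 is 10/(1 - f): 11.1 at f = 10% and 12.5 at f = 20%. At the planned 1 subject per month, that is 1.1 to 2.5 extra months.

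**The case against.** **Intent.** Much of the text points to exposed subjects. Section 2.5.3 ties the toxicities to those occurring "with the radiation regimen of 6 Gy per day for 5 fractions". Section 3.1 plans radiation for everyone, and section 13.2.3 names radiation as the investigational agent, which could let section 8.2 be read as allowing replacement. This stands as evidence of intent, but none of it defines the denominator. Two teams could compute different incidences from the same data.

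**Section 12.6.1.** A reader might infer that this section itself places unirradiated subjects in the run-in. It does not: it sets when toxicity observation starts, and an inclusive safety population is normal practice. The gap lies in the wording of the run-in rule.

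**Frequency.** Non-irradiation should be uncommon. Simulation and planning take place at screening (6.1.1), fractions are scheduled for Cycle 1 Days 1-5 (6.1), and section 4.3 excludes patients with a contraindication to radiation or who cannot tolerate positioning. This stands. A reader might take the gap between 42 enrolled and 34 evaluable (8/42 = 19%) as the missing rate, but the plan does not break that gap down by reason, so it cannot serve.

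**Likely event rates.** Section 2.5.1 describes severe pneumonitis as uncommon and the dose as conservative. At low true rates the absolute loss is small: with 10% unirradiated and a true 10% rate, the trigger chance is 6.2% instead of 7.0%.

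**Other oversight.** The DSMB receives reports every 6 months and can convene as needed, the study team reviews adverse events monthly, and there is an independent medical monitor (section 14). These are real but partial backstops; none of them fixes who is counted.

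**Conclusion.** The point holds as a defect in how the run-in denominator is written, and it should be corrected. If one or two of the 10 are never irradiated, the chance of triggering at a true 30% rate falls from 61.7% to 53.7-55.1% or 44.8-47.8%. At a true 20% it falls from 32.2% to 26.2-27.7% or 20.3-23.3%. These figures rest on the literal reading, on an assumed 0 to 2 unirradiated subjects, and on a background rate of 0% to 5%. If every counted subject is irradiated, nothing is lost.

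A reader might go further and conclude that the run-in will be substantially diluted, or that an unsafe dose will probably be missed for this reason. The documents do not support that: they give no rate of non-irradiation, and their screening steps suggest it is low. The cohort size is the larger limit, because even with all 10 irradiated the rule misses a true 30% rate 38% of the time. The efficacy sample size is unaffected.

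**What to change.** In sections 1, 2.5.3, 3.1, 12.1 and 14.1:

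- Define the run-in cohort, and the following 10 at 5 Gy, as the first 10 subjects who receive at least one radiation fraction at that dose level.
- Replace never-irradiated subjects for this rule only.
- In the counted subjects, include every qualifying grade 3 or higher event from first study treatment, including immune-mediated events before the first fraction. Starting the count at the first fraction would discard events the rule is meant to capture in subjects who begin radiation late.
- Report qualifying events in never-irradiated subjects to the DSMB separately, so that someone who leaves because of an early immune-mediated event is not lost from view.

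Section 12.6.1 and the 30% threshold can stay as they are.

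The cost is about 1 to 2.5 months of extra accrual to fill the cohort if 10-20% are never irradiated, and none if all are. The chance of an unneeded dose reduction at a true 10% rate rises from 5.4-6.2% to 7.0%. A subject who receives only one fraction still counts, so some dilution from partial treatment remains.
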